9.4.3 Safety Analyses

All safety analyses will be based on the safety analysis population grouped according to the treatment assigned at randomization. Analysis methods are summarized in Table 9.

 Table 9
 Safety Statistical Analysis Methods

Endpoint	Statistical Analysis Methods
Adverse events	The original terms recorded on the eCRF by the Investigator for AEs will be coded by the Sponsor. AEs will be summarized by mapped term and appropriate thesaurus level.
Clinical laboratory tests	All clinical laboratory data will be stored on the database in the units in which they were reported. Participant listings and summary statistics at each assessment time will be presented using the International System of Units (SI units; Système International d'Unités). Laboratory data not reported in SI units will be converted to SI units before processing.
	Laboratory test values will be presented by individual listings with flagging of values outside the normal ranges.
Vital signs	Vital signs data (including orthostatic changes) will be presented by individual listings with flagging of values outside the normal ranges and flagging of abnormalities. In addition, tabular summaries or averaged graphs will be used, as appropriate.
ECG data analysis	ECG data will be presented by individual listings. In addition, tabular descriptive summaries for the change from baseline in ECG intervals: heart rate, PQ (PR), QRS, QT, RR, QTcF, T- and U-waves will be displayed
Concomitant medications	The original terms recorded on the participants' eCRF by the Investigator for concomitant medications will be standardized by the Sponsor by assigning preferred terms.
	Concomitant medications will be presented in summary tables and listings.
C-SSRS	C-SSRS data will be presented by individual listings.
ESRS-A	ESRS-A data will be presented by individual listings.

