6.1 TREATMENTS ADMINISTERED

Table 5 summarizes the treatments administered. Of note, the daily dose of study drug has been increased in Part B of the study (*from* protocol Version 5: RO6889450, or placebo).

Table 5 Summary of Treatments Administered

Study Part A				
Study Drug Name:		RO6889450 (IMP)	RO6889450 (placebo; IMP)	
Dosage Formulation:		Hard capsules	Hard capsules	
Strength:			N/A	
Route of Administration:		Oral	Oral	
Dosing Instructions:		3 capsules QD	3 capsules QD	
Daily Dose of RO6889450			NA	
Packaging and Labeling ^a		HDPE bottle	HDPE bottle	
Storage Conditions		Do not store above 30°C, protect from light, keep container tightly closed.	Do not store above 30°C, protect from light, keep container tightly closed.	
	Study Part B (prior to	Protocol Version 5)		
Study Drug Name:	RO6889450 (IMP)	RO6889450 (IMP)	RO6889450 (placebo; IMP)	
Dosage Formulation:	Hard capsules	Hard capsules	Hard capsules	
Strength:			N/A	
Route of Administration:	Oral	Oral	Oral	
Dosing Instructions:	3 capsules QD	3 capsules QD	3 capsules QD	
Daily Dose of RO6889450			NA	
Packaging and Labelinga	HDPE bottle	HDPE bottle	HDPE bottle	
Storage Conditions	Do not store above 30°C, protect from light, keep container tightly closed.	Do not store above 30°C, protect from light, keep container tightly closed.	Do not store above 30°C, protect from light, keep container tightly closed.	

Table 4 Summary of Treatments Administered (cont.)

Study Part B (from Protocol Version 5)				
Study Drug Name:	RO6889450 (IMP)	RO6889450 (placebo; IMP)		
Dosage Formulation:	Hard capsules	Hard capsules		
Strength:		N/A		
Route of Administration:	Oral	Oral		
Dosing Instructions:	Patients will take 3 capsules from each of two bottles (total 6 capsules) once daily, preferably in the morning, with or without food.			
arm	3 capsules and	3 capsules placebo QD		
arm	6 capsules QD (three from each of two bottles)	N/A		
Placebo arm	N/A	6 capsules QD (three from each of two bottles)		
Daily Dose of RO6889450		NA		
Packaging and Labeling ^a				
arm	1 HDPE bottle	1 HDPE bottle		
arm Placebo arm	2 HDPE bottles N/A	N/A 2 HDPE bottles		
Storage Conditions	Do not store above	Do not store above		
Storage Conditions	30°C, protect from light, keep container tightly closed.	30°C, protect from light, keep container tightly closed.		

Abbreviations: HDPE = high density polyethylene; IMP = investigational medicinal product; N/A = not applicable; QD = once a day

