6.2 PREPARATION/HANDLING/STORAGE/ACCOUNTABILITY

Study drug packaging will be overseen by the Roche clinical trial supplies department.

The packaging and labeling of the IMPs will be in accordance with Sponsor standard and local regulations.

The investigational site will acknowledge receipt of IMPs and confirm the shipment condition and content. Any damaged shipments will be replaced.

Upon arrival of the IMPs at the site, site personnel will complete the following:

- Check the IMPs for damage.
- Verify proper identity, quantity, and integrity of seals.
- Report any deviations or product complaints to the study monitor upon discovery.

For the placebo compliance period, the bottles are open-label and the batch number is the identifier. The qualified individual responsible for dispensing will dispense the batch number assigned to a participant by the IxRS.

Each double-blind bottle of capsules will be labeled with a unique medication number (MEDNO). The qualified individual responsible for dispensing the study drug will dispense the correct bottles of IMP to the participant at each dispensing visit by matching the MEDNOs allocated by the IxRS for that visit with the number printed on the IMP label.

Only participants enrolled in the study may receive study drug and only authorized site staff may supply or administer IMP. If the IMP dispensing visit cannot take place in the clinic (e.g., due to travel restriction due to an outbreak of COVID-19) and alternatives methods of delivery are not feasible, the IMP dispensing may be done with direct site to patient shipment (with a prior approval from relevant health authority if applicable). All IMPs must be stored in a secure, environmentally controlled, and monitored (manual or automated) area in accordance with the labeled storage conditions with access limited to the Investigator and authorized site staff. Any deviations or product complaints should be reported to the study monitor upon discovery.

The Investigator, Institution, or the Head of the Medical Institution (where applicable) is responsible for IMP accountability, reconciliation, and record maintenance (i.e., receipt, reconciliation and final disposition records).

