6.4 TREATMENT COMPLIANCE

The qualified site personnel will dispense the correct bottles of IMP according to the visits outlined in the Schedule of Activities (SoA; see Section 1.3) and according to the IxRS instructions (see Section 6.2). This individual will write the date dispensed and

participant number on the IMP label. To improve compliance bottles will be marked as Bottle A and Bottle B. This individual will also record the unique batch numbers for the placebo compliance period or MEDNOs for the double-blind period received by each participant in the participant's records. Treatment compliance verification will be done using the medication adherence platform via a smartphone app (see Section 6.4.1) and will also be checked by the site.

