9.3 POPULATIONS FOR ANALYSES

For purposes of analysis, the following populations are defined in Table 7.

Table 7 Analysis Populations

Population	Description
Modified intent-to-treat (ITT)	All randomized participants who have received at least one dose of study drug will be included in the efficacy population.
Per-protocol	All randomized participants who finished 12 weeks of treatment without any major protocol violations and acceptable compliance
Safety	Same as modified ITT population.
Pharmacokinetic	All participants who have received at least one dose of study drug and who have data from at least one post-dose sample will be included in the PK analysis population. Participants will be excluded from the PK analysis population if they significantly violate the inclusion or exclusion criteria, deviate significantly from the protocol, or if data are unavailable or incomplete that may influence the PK analysis. Excluded cases will be documented together with the reason for exclusion. All decisions on exclusions from the analysis will be made prior to database closure.

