**Table 2 Analysis Populations**

Population	Description
Modified intent-to-treat (ITT)	All randomized participants who have received at least one dose of study drug, including participants who were withdrawn prematurely, will be included in the efficacy population. The modified ITT analysis population will be the primary analysis population for all efficacy data analyses.
Per-protocol (PP)	No PP analysis population is defined for Part A
Safety evaluable (SE)	Same as modified ITT analysis population.

Pharmacokinetic (PK)	All participants who have received at least one dose of study drug and who have data from at least one post-dose sample will be included in the PK analysis population. Participants will be excluded from the PK analysis population if they significantly violate the inclusion or exclusion criteria, deviate significantly from the protocol, or if data are unavailable or incomplete that may influence the PK analysis. Excluded cases will be documented together with the reason for exclusion. All decisions on exclusions from the analysis will be made prior to database closure.
----------------------	--

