### 4.6.1 Exposure of Study Medication

The following extent of exposure to randomized study medication will be summarized by randomized treatment arm:

- Duration of treatment (weeks), which will be calculated from the first day of randomized double-blind study medication intake as recorded with AICURE to the last day of randomized double-blind study treatment intake as recorded with AICURE, i.e. last dosing date minus first dosing date plus 1 day (divided by 7 to get weeks).
- Number of doses over the whole double-blind treatment period derived from the number of days at which randomized double-blind treatment was taken as recorded with AICURE.
- Total cumulative dose (mg) over the whole double-blind treatment period as

recorded with AICURE.

- Extent of compliance with randomized double-blind treatment (%). Treatment compliance for each participant will be calculated as actually taken dose divided by planned dose of double-blind treatment. The actually taken dose will be the total cumulative dose. The planned dose is the cumulative planned dose over 84 days, i.e., [REDACTED] x84 days.

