#### **4.6.2 Adverse Events**

The original terms recorded on the eCRF by the Investigator for AEs will be assigned by the Sponsor to a standardized term (the “preferred term”) based on MedDRA. All data displays of AE will be performed using the system organ class and preferred terms. All AEs will be presented as frequency tables by randomized treatment arm with numbers and percentage of participants experiencing AEs.

AEs will be separately summarized for the following analysis periods:

- Screening/Wash-out period for antipsychotics includes the AEs with onset before the first day of study medication in the randomized double-blind treatment period (Baseline Sign and Symptoms).
- Double-blind treatment period including follow-up includes all AEs from day of first onset of study medication in the double-blind treatment period until end of follow-up.

Intensity and relationship to study treatment will be summarized for the double-blind treatment period including follow-up as assigned by the investigator.

In the summary table of AEs by intensity, if a participant has more than one occurrence of an event, the event with the most severe intensity will be counted. If the intensity of an AE is missing, then the AE will be included only in the total number of events column and not in the count of participants with the event by intensity.

In the summary table of AEs by relationship to trial treatment, if a participant has more than one occurrence of an event, the most closely related event will be counted. If the relationship of an AE is missing, then the AE will be included only in the total number of events column and not in the count of participants with the event by relationship.

All SAEs and AEs that led to death, and AEs that led to withdrawal of study treatment will also be summarized by treatment arm.

The following rules will be applied for AEs with missing onset or end dates:

- Events that are missing both, onset and end dates, will be considered as emerging from treatment, given the participant had at least one dose of study medication.
- If the onset date is missing and the end date is on or after the first dosing date, then the event will be considered as emerging from treatment.
- If the end date is missing and the onset date is on or after the first dosing date of a specific period, then the event will be considered as emerging from treatment.

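### Safety is grouped by assigned treatment with no as-received rule, so if a participant were given the wrong study drug their events would be counted under a treatment they did not take

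*Protocol*

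**What the plan says.** Protocol 9.4.3 states: "All safety analyses will be based on the safety analysis population grouped according to the treatment assigned at randomization". The section is not limited to one part, so it governs Part A and Part B. SAP 4.6, which covers Part A only, carries the same sentence. The rule recurs at the end of SAP 4.6.2 to 4.6.7 and 4.6.9.

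The tables follow the same grouping. For adverse events (SAP 4.6.2): "All AEs will be presented as frequency tables by randomized treatment arm with numbers and percentage of participants experiencing AEs". For exposure (SAP 4.6.1): "The following extent of exposure to randomized study medication will be summarized by randomized treatment arm". The mean plots in SAP 4.6.3, 4.6.4 and 4.6.9 are also drawn by randomized arm.

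The population definition does not change this. The protocol's analysis-population table in 9.3 defines the safety population as "Same as modified ITT population", and SAP Table 2 says "Same as modified ITT analysis population". That set is everyone randomized who took at least one dose. Receipt of drug decides who is in the set, and assignment decides the column in which they are counted.

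I found no as-received rule, no as-received sensitivity table and no listing of participants whose assigned and received treatments differ. A separate analysis plan for Part B is announced in SAP section 1 but was not supplied.

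**The concern.** Grouping by assignment protects the randomized comparison for efficacy. For safety, the usual question is what happened to people who took the drug. If a participant assigned to placebo is given active drug, their drug-related events go into the placebo column. If a participant assigned to active drug is given placebo, the active column is diluted. For any event that the drug makes more frequent, both errors shrink the difference between drug and placebo, which is the unsafe direction for a safety comparison.

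Part B adds a second route. Under the kit scheme in use from protocol Version 5 (section 6.1), each participant takes three capsules from each of two bottles, and the arms differ in whether two, one or neither bottle holds active drug. A wrong bottle could therefore give the wrong dose as well as the wrong treatment, and assigned grouping would blur the contrast between the two dose arms. That route does not exist in Part A, which has one active arm.

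**Working it through.** The plan states no figure on this point, so there is nothing to reproduce. The check covers how much one participant can matter.

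**Inputs**
- Part A: 27 randomized (SAP section 1), 1:1 allocation (SAP 3.1). The split is not given, so 13 and 14 per arm is an assumption.
- Part B: about 200 participants over three arms, plus about 20 in Japan (Protocol 9.2). This gives 200/3 ≈ 67 or 220/3 ≈ 73 per arm.
- Event rates and error rates: none in the documents. Those used below are assumptions.

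**Share of an arm**
- Part A: 1/13 = 7.7%; 1/14 = 7.1%.
- Part B: 1/67 = 1.5%; 1/73 = 1.4%.

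**Regrouping one participant who had the event (Part A).** If an arm of 13 has x events and one event-bearing participant leaves it, its rate changes by x/13 − (x−1)/12 = (13−x)/156.
- x = 1: 12/156 = 7.7 points.
- x = 6: 7/156 = 4.5 points.

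The receiving arm goes from 14 to 15 and changes by (x+1)/15 − x/14 = (14−x)/210, which is at most 14/210 = 6.7 points. So 7.7 points is a ceiling, reached only when nobody else in the arm had the event.

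**Expected bias.** Let pD and pP be the true event rates on drug and placebo, and let f be the fraction of the placebo arm that took drug throughout. Assigned grouping then shows a placebo rate of pP(1−f) + pD·f, so the difference becomes (pD − pP)(1−f).

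| Assumed drug vs placebo | True difference | 1 of 13 (Part A) | 1 of 67 (Part B) |
|---|---|---|---|
| 10% vs 2% | 8.0 points | 7.4 | 7.9 |
| 20% vs 5% | 15.0 points | 13.8 | 14.8 |
| 40% vs 20% | 20.0 points | 18.5 | 19.7 |

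In the middle row, five of 67 would give 13.9 points. These figures assume the wrong treatment was taken for the whole period. The Part B schedule dispenses drug at Days 1, 14, 28, 42 and 56, so a single wrong bottle would be replaced at the next dispensing visit and would matter less.

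**No error.** With f = 0 the two rules give the same tables.

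**The case against.** The strongest case on the other side is that the problem is hypothetical and well guarded. The IxRS allocates numbered bottles, and site staff match the numbers at each dispensing visit (Protocol 6.2). The numbers are written in the participant's records (6.4). The adherence platform confirms the participant's identity and the medication to be taken (6.4.1). PK samples are taken repeatedly, and the bioanalyst has the randomization list (6.3.2). Medication errors go on the adverse event form whether or not an event follows (Appendix 2, section 5.2). Part A is a descriptive report on 27 people with no hypothesis tests (SAP section 4), and it also summarizes major protocol violations (SAP 4.2.3). A reader could find a single misallocated participant there.

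Most of this stands. The controls make an error less likely and easier to trace. They do not move anyone to the right column of a summary table. They also show that the information needed for as-received grouping is already collected.

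Three stronger readings are tempting and are not supported:
- *That errors happened or are likely.* Neither document reports one. Protocol 6.4 says "To improve compliance bottles will be marked as Bottle A and Bottle B", but that describes a compliance aid and is not evidence of mix-ups. Multiplying 220 participants by five visits and two bottles gives 2,200, but that is not a minimum. It assumes full attendance, although Protocol 9.2 allows for about 25% non-completion. It also assumes two bottles for everyone, although Part B before Version 5 used a three-capsule regimen, and the number of bottles per visit is not stated. A count of dispensings is in any case not an error rate.
- *That one error typically shifts a Part A rate by 7 to 8 points.* That is a ceiling, as shown above.
- *That the Part B analysis is settled.* Its plan is not available and could add an as-received rule. What can be said is that the governing protocol text has none.

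**Conclusion.** The point holds as a conditional one. Assigned-treatment grouping for safety is an explicit rule in Protocol 9.4.3 and SAP 4.6, not a missing detail, and nothing in either document offsets it. If a wrong-drug error occurs, the rule places events under a treatment that was not taken. Between drug and placebo, this pulls the rates together for any event the drug makes more frequent. Between the two Part B doses, it blurs their separation.

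The size is unknown because no error rate is given, and it is probably small. One participant is at most about 7-8% of a Part A arm, on the assumed 13/14 split, and about 1.4-1.5% of a Part B arm at the planned numbers. With isolated errors and the assumed event rates, the difference shrinks by 0.6 to 1.5 points in Part A and by 0.1 to 0.3 points in Part B. It would matter most for rare serious events, where a single case in the wrong column can change how a table is read. This is a free improvement and not a threat to the trial's conclusions.

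**What to change.** - In Protocol 9.4.3 and SAP 4.6, group safety by treatment actually received. Make the same change to the repeated sentences in SAP 4.6.2 to 4.6.7 and 4.6.9, and to the randomized-arm wording for exposure, adverse events and plots in 4.6.1 to 4.6.4 and 4.6.9. Changing only the lead sentence of 4.6 would leave the SAP contradicting itself.
- State the mixed-exposure rule in advance. Participants who took their assigned treatment for most of the period stay in that arm; those who received a different treatment throughout are grouped by what they received. The text should also say where someone falls who took a different treatment for most, but not all, of the period. Grouping by the highest active dose ever received is not a good substitute, because one wrong bottle would move a placebo participant's events from before the error into an active arm.
- List every participant whose assigned and received treatments differ, with the timing of events relative to the error.
- Carry the same rule into the Part B analysis plan, and keep assigned treatment for efficacy.

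The cost is minor rewording in several SAP subsections and some programming. The bottle numbers and medication-error records are already collected, and nothing is lost if dispensing is free of error.

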9.4.4 Pharmacokinetic Analyses

Population PK analyses using nonlinear mixed effects modeling will be performed as described in Section 8.5.

The results of the analysis will be reported separately from the CSR.

9.5 INTERIM ANALYSES

The Sponsor may choose to conduct an interim efficacy analysis in Part A. The decision to conduct an optional interim analysis and the timing of the analysis will be documented in the Sponsor's trial master file prior to the conduct of the interim analysis. The interim analysis will be performed and interpreted by members of the Sponsor study team and appropriate senior management personnel who will be unblinded at the treatment group level. Access to treatment assignment information will follow the Sponsor's standard procedures.

The results of this analysis may support initiation of Part B enrollment during Part A if a positive results threshold is met as defined in the SAP. In case of very slow recruitment, Part A may be stopped and/or Part B may be started without the interim analysis.

The Sponsor may choose to conduct up to two additional interim efficacy analyses of Part B to determine the chance of final success. The decision to conduct an optional interim analysis and its timing will be documented in the Sponsor's trial master file prior to the conduct of the interim analysis. The interim analysis will be performed and interpreted by members of the Sponsor study team who will be unblinded at the treatment group level. The results of such an analysis may support an early termination of Part B. Access to treatment assignment information will follow the Sponsor's standard procedures.

The planned interim analyses will be described in detail separately. An iDMC will review unblinded safety and efficacy (as appropriate) data, as outlined in the "iDMC charter". Additional ad-hoc meetings may be convened to evaluate safety.

9.6 SUMMARIES OF CONDUCT OF STUDY

The number of participants screened and the total number of participants randomized will be reported. The number of participants prematurely withdrawn from study drug and the study will be reported.

